# 3.0 OBJECTIVES

The objective of this study is to evaluate the efficacy, safety, and tolerability of rapastinel relative to placebo in the prevention of relapse in patients with MDD.

## Efficacy Objectives

• Primary efficacy objective: To evaluate the efficacy of rapastinel (225 or 450 mg IV weekly or clinically driven schedule) versus placebo in the maintenance treatment of MDD as a monotherapy, as measured by time to relapse during the first 52 weeks of the DBTP.

# 4.0 PATIENT POPULATIONS

The following analysis populations will be considered in the statistical analysis of the study.

#### 4.1 OPEN-LABEL SAFETY POPULATION

The Open-label Safety Population will consist of all patients who signed the informed consent form (ICF) and received at least 1 dose of open-label rapastinel during the OLTP of the study.

#### 4.2 OPEN-LABEL MODIFIED INTENT-TO-TREAT POPULATION

The Open-label modified Intent-to-Treat (OL mITT) Population will consist of all patients in the Open-label Safety Population who had at least 1 postbaseline assessment of the MADRS during the OLTP of the study. An assessment is considered postbaseline in the OLTP if it was taken after the first dose of open-label rapastinel during the OLTP of the study.

#### 4.3 DOUBLE-BLIND SAFETY POPULATION

The Double-blind Safety Population will consist of all patients in the Open-label Safety Population who were randomized to a treatment group during the DBTP of the study and received at least 1 dose of double-blind IP.

## 4.4 DOUBLE-BLIND MODIFIED INTENT-TO-TREAT POPULATION

The Double-blind modified Intent-to-Treat (DB mITT) Population will consist of all patients in the Double-blind Safety Population who had at least 1 post-randomization assessment of the MADRS or the CGI-S during the DBTP of the study.

# 5.0 PATIENT DISPOSITION

The number of patients who were screened for participation in the OLTP from lead-in studies RAP-MD-30 and RAP-MD-32, and who were screen failures and reasons for failing will be summarized.

The number of patients in the Open-label Safety and Open-label mITT Populations will be summarized overall and by study center. The number of patients in the Double-blind Safety and Double-blind mITT Populations will be summarized overall, and by treatment group by study center.

The number and percentage of patients who entered the OLTP, who prematurely discontinued from the OLTP, who completed the OLTP, who met or did not meet the criteria to enter the DBTP at the end of the OLTP, and who entered the DBTP will be summarized overall and by reasons for premature discontinuation for all enrolled patients in the OLTP.

Similarly, the number and percentage of patients who completed the DBTP and who prematurely discontinued from the DBTP will be summarized overall, by double-blind treatment group, and by reasons for premature discontinuation for the all randomized patients in the DBTP.

## 6.0 DEMOGRAPHICS AND BASELINE CHARACTERISTICS

Demographic parameters (e.g., age, race, ethnicity, sex,) and baseline characteristics (e.g., weight, height, body mass index) will be summarized overall for the Open-label mITT Populations and by treatment group for the Double-blind modified ITT population.

Medical and surgical history during the past 12 months and psychotropic medication history during the previous 5 years will be coded using the Medical Dictionary for Regulatory Activities (MedDRA), version 21.0 or newer. Data will be presented in listings for the Open-label Safety Population.

Psychiatric history will be summarized overall for the Open-label mITT Populations and by treatment group for the Double-blind modified ITT population.

*Prior medication* is defined as any medication started before the date of first dose of open-label IP. *Concomitant medication* during the OLTP is defined as any medication taken on or after the date of the first dose of open-label IP during the OLTP. Concomitant medication during the DBTP will be defined as any medication taken on or after the date of the first dose of double-blind IP.

Prior and concomitant medications during the OLTP will be listed for the Open-label Safety Population. Concomitant medications during the DBTP will be listed for the Double-blind Safety Population. Concomitant medications started after the patient's last study visit during their last treatment period will be presented in the data listings.

The *World Health Organization Drug Dictionary Enhanced* (WHODDE) will be used to classify prior and concomitant medications by therapeutic class and drug name.

#### 7.0 EXTENT OF EXPOSURE AND TREATMENT COMPLIANCE

#### 7.1 EXTENT OF EXPOSURE

Exposure to open-label rapastinel for the Open-label Safety Population during the OLTP will be summarized for treatment duration, calculated as the number of days from the date of the first dose of open-label rapastinel taken to the date of the last dose taken during the OLTP, inclusive. Descriptive statistics will be presented.

Exposure to double-blind IP for the Double-blind Safety Population during the DBTP will be summarized for treatment duration, calculated as the number of days from the date of the first dose of double-blind IP taken to the date of the last dose taken during the DBTP, inclusive. Descriptive statistics will be presented by treatment group.

The number of IV doses of rapastinel administered to each patient during the OLTP will be summarized using descriptive statistics for the Open-label Safety Population. Similarly, the number of IV doses administered to each patient during the DBTP will be summarized by treatment group, using descriptive statistics for the Double-Blind Safety Population.

#### 8.0 EFFICACY ANALYSES

#### 8.1 PRIMARY EFFICACY PARAMETERS

The analysis of the primary efficacy parameter will be performed using the Double-blind mITT Population.

The primary efficacy parameter is the time to first relapse during the 52 weeks of the DBTP, defined as the number of days from the randomization date of DBTP to the relapse date (ie., relapse date – randomization date + 1). Relapse during the DBTP is defined as meeting any of the following criteria:

- Rater-administered MADRS total score  $\geq 18$  at 2 consecutive visits
- $\geq 2$  increase in CGI-S score compared with that obtained at randomization
- Risk of suicide as determined by the investigator
- Need for hospitalization due to worsening of depression as determined by the investigator
- Need for alternative treatment of depressive symptoms as determined by the investigator

Patients who did not meet the above relapse criteria during the 52 weeks of the DBTP, the time to relapse will be censored at the time of completion or discontinuation from the study, or 52 weeks, whichever is earlier.

The primary efficacy analysis will be presented by the cumulative distribution function of time to relapse characterized by the Kaplan-Meier curve for each treatment group.

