#### **9.7.5 Efficacy Analyses**

All efficacy analyses for the OLTP will be performed using the Open-label mITT Population. All efficacy analyses for the DBTP will be performed using the Double-blind mITT Population. The baseline of the lead-in study will be used as the baseline for the OLTP and the DBTP. All statistical tests will be 2-sided hypothesis tests performed at the 5% level of significance and all confidence intervals (CIs) will be 2-sided 95% CIs, unless stated otherwise.

An additional analysis plan specific to European Medicines Agency will be presented in a stand-alone document.

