**9.7.5.1 Primary Efficacy Analyses**

The primary efficacy parameter is the time to first relapse during the 52 weeks of the DBTP, defined as the number of days from the randomization date of DBTP to the relapse date during the 52 weeks of the DBTP. Relapse during the DBTP is defined as meeting any of the following criteria:

- MADRS total score  $\geq 18$  at 2 consecutive visits
- $\geq 2$  increase in CGI-S score compared with that obtained at randomization
- Risk of suicide as determined by the investigator
- Need for hospitalization due to worsening of depression as determined by the investigator
- Need for alternative treatment of depressive symptoms as determined by the investigator

For patients who did not meet the above relapse criteria during the 52 weeks of the DBTP, the time to relapse will be censored at the time of completion or discontinuation from the study, or 52 weeks, whichever is earlier.

The primary efficacy analysis will compare the time to first relapse between placebo and rapastinel treatment groups in the respective time-frame (within the 52 weeks of the DBTP) using the log-rank test. The primary null hypothesis is that the distribution of the time to relapse for each of the rapastinel treatment groups is not different from that for the placebo treatment group.

Estimates of the hazard ratio and 95% CI will be based on the Cox proportional hazards model with treatment group as an explanatory variable. The cumulative distribution function of time to relapse will be characterized by the Kaplan-Meier curves.

The Hochberg procedure will be used to control the overall type I error rate at the 0.05 level for comparisons between each of rapastinel treatment groups and the placebo.

[REDACTED]

• [REDACTED]

[REDACTED]

[REDACTED]

[REDACTED]

[REDACTED]

[REDACTED]

[REDACTED]

[REDACTED]

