## **12.0 DETERMINATION OF SAMPLE SIZE**

The sample size and power calculations are based on the analysis of time to relapse during the first 52 weeks of the DBTP. Assuming a relapse rate of 19% per 26 weeks in the placebo group and a dropout rate of 20% per 26 weeks in all treatment groups, the sample size of 200 per group will have 90% power to detect a hazard ratio of 0.475 for a rapastinel treatment versus placebo at a 0.05 significance level. To achieve this number of randomized patients, approximately 1400 patients need to be enrolled in this study if 50% of patients are qualified for randomization.

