#### 14.1 SUMMARY STATISTICS

The following statistical summaries will be presented for each type of data:

- Continuous variables will be summarized by descriptive statistics (number of patients, mean, standard deviation (SD), median, minimum, and maximum values).
- Categorical variables will be summarized by frequency distributions (counts and percentages).
- Time-to-event data will be summarized by showing the number of patients, number of patients experiencing the event of interest, estimates of the median, first quartile and third quartile using the Kaplan Meier estimate as well as a 95% CI for the median

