#### 15.0 CHANGES TO ANALYSES SPECIFIED IN PROTOCOL

Analyses and output have been limited to those needed to support the writing of an abbreviated CSR. The major changes to the analyses specified in the original protocol, dated 02MAY2018, are as follows:

• The primary efficacy analysis will be performed via the Kaplan-Meier curve for the cumulative distribution function of time to relapse for each treatment group.

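### The SAP keeps a versus-placebo objective and a 90% power statement, but its readable text plans no estimate or test of rapastinel against placebo

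*SAP*

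**What the plan says.** Protocol 9.7.5.1 plans a log-rank comparison of each rapastinel group with placebo, with Hochberg control at 0.05 overall. It also plans an effect estimate: "Estimates of the hazard ratio and 95% CI will be based on the Cox proportional hazards model with treatment group as an explanatory variable".

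The SAP changes this. Section 8.1 says: "The primary efficacy analysis will be presented by the cumulative distribution function of time to relapse characterized by the Kaplan-Meier curve", one for each treatment group. Section 15.0 lists the same thing as a major change from the protocol and gives the reason: "Analyses and output have been limited to those needed to support the writing of an abbreviated CSR". For time-to-event data, section 14.1 plans "showing the number of patients, number of patients experiencing the event of interest, estimates of the median, first quartile and third quartile", plus a 95% CI for the median. All of these are within-arm quantities.

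Two other parts of the SAP were left as they were. The primary objective in section 3.0 is still rapastinel "versus placebo in the maintenance treatment of MDD as a monotherapy, as measured by time to relapse". Section 12.0 still says that 200 patients per group "will have 90% power to detect a hazard ratio of 0.475 for a rapastinel treatment versus placebo at a 0.05 significance level".

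**The concern.** Patients were randomized 1:1:1 to answer a question against placebo. As the SAP reads, the report would show three curves and some within-arm summaries, with no effect estimate, no interval for a difference and no test. A reader who wants the treatment difference must build it from event counts, which ignore follow-up time, or read it off curves that carry no interval for the difference.

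The retained objective and power text also lead the reader to expect a comparison that the report will not contain. Section 15.0 says what the primary analysis becomes. It does not say that the test, the hazard ratio and the multiplicity control are dropped; that has to be inferred from their absence.

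**Working it through.** **Inputs (SAP 12.0, same in Protocol 9.7.10).** Placebo relapse is 19% per 26 weeks, with "a dropout rate of 20% per 26 weeks in all treatment groups". Hazard ratio 0.475, 200 per group, 52 weeks of follow-up. I assume exponential times and apply 0.475 to both rapastinel arms.

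**Weekly hazards.**
- Placebo relapse: h = -ln(0.81)/26 = 0.008105
- Rapastinel relapse: 0.475 × 0.008105 = 0.003850
- Dropout: d = -ln(0.80)/26 = 0.008582

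**Expected events by Week 52.** The formula is 200 × h/(h+d) × (1 - exp(-52(h+d))).
- Placebo 56.3 and rapastinel 29.5, together 85.8 per comparison.

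**The plan's own figure.** With 85.8 events and two-sided 0.05, Freedman's formula gives √85.8 × (1 - 0.475)/(1 + 0.475) = 3.30. Subtracting 1.96 leaves 1.34, which is power of 90.9%. The unpooled log hazard ratio variance gives 90.6%, Lachin-Foulkes 91.2%, Schoenfeld 93.2%, and a simulated log-rank test 92.2%. The 90% statement therefore describes a pairwise time-to-event comparison with placebo, which the SAP no longer plans.

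**Can the planned within-arm summaries replace the contrast?**

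| Quantity | Formula | Placebo | Rapastinel |
|---|---|---|---|
| Kaplan-Meier relapse, Week 26 | 1 - exp(-26h) | 19.0% | 9.5% |
| Kaplan-Meier relapse, Week 52 | 1 - exp(-52h) | 34.4% | 18.1% |
| Crude relapse | events/200 | 28.2% | 14.7% |
| First quartile time | -ln(0.75)/h | 35.5 weeks | 74.7 weeks |
| Median time | ln(2)/h | 85.5 weeks | 180 weeks |

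No median falls within 52 weeks, and the third quartile lies later still. Only the placebo first quartile is reached. A rapastinel arm would reach its first quartile only if its hazard ratio exceeded -ln(0.75)/(52 × 0.008105) = 0.68.

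**Counts and dropout.** Take two arms with the same placebo relapse hazard and assume dropout of 10% in one and 30% in the other per 26 weeks. These rates are my assumption; the plan assumes equal dropout. The events formula gives crude relapse of 31.2% and 25.2%, a 6.0-point gap caused by dropout alone.

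**What the missing estimates would look like at planned size.**
- Hazard ratio 95% CI: exp(ln 0.475 ± 1.96 × √(1/56.3 + 1/29.5)) = 0.30 to 0.74.
- Kaplan-Meier differences, with variance per arm S² × h/(n(h+d)) × (exp((h+d)t) - 1), where S = exp(-ht) and n = 200:
  - Week 26: 9.5 points (95% CI 2.3 to 16.7)
  - Week 52: 16.2 points (95% CI 6.7 to 25.8)

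**If far fewer events accrued.** The documents do not give the number reached. The same formula at an observed hazard ratio of 0.475 gives:

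| Assumed events | Split equally | Split in the design ratio |
|---|---|---|
| 20 | 0.20 to 1.14 | 0.19 to 1.20 |
| 40 | 0.26 to 0.88 | 0.25 to 0.91 |

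**The case against.** The strongest reply is that this is a declared scope decision. Section 15.0 names the change and gives a reason, and an abbreviated report may legitimately describe the arms without inference. The power text sits under the sample size heading and can be read as a record of the design. This stands in part: the absence of a formal test is not in itself an error, and there is no concealment. It does not explain why the effect estimate is dropped while curves from the same data are kept, or why section 3.0 was left unreconciled.

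A second reply is that the SAP text is incomplete, and Protocol 9.7.5 adds: "An additional analysis plan specific to European Medicines Agency will be presented in a stand-alone document". That plan is not among the documents and is not judged here. For the primary analysis, however, sections 8.1 and 15.0 are readable and agree with each other.

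Third, the illustrations have limits, and these are fair:
- No crude percentage is planned as the efficacy result. The Kaplan-Meier curves handle censoring, and SAP 5.0 tabulates discontinuations by arm, so unequal dropout would be visible. The 6.0-point example shows only why counts cannot serve as the contrast.
- An equal split of events sits awkwardly with a hazard ratio of 0.475 in arms of equal size, so the design-ratio intervals are the more coherent ones. They differ little.
- In the clinically driven arm, patients judged stable receive placebo (Protocol 9.1.2). Its hazard may resemble placebo early on, and a single hazard ratio may summarize it poorly. Reporting Kaplan-Meier differences alongside helps.
- At planned size about 200 × exp(-52 × (0.008105 + 0.008582)) = 84 placebo patients would remain at risk at Week 52. With fewer patients the Week 52 estimate would be fragile.

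**Conclusion.** The concern holds and should be fixed. Under the readable SAP, relapse can be described by arm but the randomized contrast is neither estimated nor tested, while the objective and power statement still promise a comparison. The planned quartiles and counts do not fill the gap under the plan's own assumptions. The finding itself rests on the wording of SAP 3.0, 8.1, 12.0, 14.1 and 15.0. The sizes rest on exponential times, the design rates and 200 per arm; actual enrolment and events are not in the documents. Because the change is disclosed and the curves are kept, this is a correctable gap and not a fatal one.

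**What to change.** 1. In SAP 8.1 and 15.0, add the protocol's Cox hazard ratio with 95% CI for each rapastinel arm against placebo.
2. In SAP 14.1, add Kaplan-Meier relapse proportions at Weeks 26 and 52 and their differences from placebo, each with 95% CI, from the dataset used for the curves. The differences are an addition to the readable protocol analysis. Show numbers at risk beside them.
3. Choose one of two positions and state it:
   - (a) keep the protocol's log-rank test with Hochberg as specified; or
   - (b) label the estimates descriptive, give no p-values, and say in sections 3.0 and 12.0 that the analysis is descriptive and the power statement only records the original design.

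Option (b) fits the declared abbreviated report. With either option, section 15.0 should say explicitly which protocol analyses are kept and which are dropped.

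The cost is SAP wording and one small table, with no new data. The downside is that with few events the interval would be wide and could be over-read; the descriptive label limits that risk.

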## 9.1 ADVERSE EVENTS

AEs will be coded using the Medical Dictionary for Regulatory Activities.

An AE (classified by preferred term) that occurs during the OLTP or thereafter will be considered a treatment-emergent adverse event (TEAE) if it was not present before the date of the first dose of IP in the lead-in study or was present before the first dose of IP in the lead-in study and increased in severity during the OLTP or thereafter. An AE that becomes serious during the OLTP or thereafter will also be considered as TEAE. If more than 1 AE is reported before the date of the first dose of IP in the lead-in study and coded to the same preferred term, the AE with the greatest severity will be used as the benchmark for comparison with the AEs occurring during the OLTP or thereafter that were also coded to that preferred term. An AE that occurs more than 30 days after the date of the last dose of IP will not be counted as a TEAE.

An AE (classified by preferred term) that occurs during the OLTP of the study will be considered a newly emergent adverse event (NEAE) if the AE was not present before the first dose of IP in the OLTP or it was present before the first dose of IP in the OLTP and increased in severity during the OLTP. An AE that becomes serious during the OLTP will also be considered as NEAE. If more than 1 AE is reported before the first dose of IP in the OLTP and coded to the same preferred term, the AE with the greatest severity will be used as the benchmark for comparison with the AEs occurring during the OLTP that were also coded to that preferred term.

An AE (classified by preferred term) that occurs during the DBTP of the study will be considered a newly emergent adverse event (NEAE) if the AE was not present before the first dose of IP in the DBTP or it was present before the first dose of IP in the DBTP and increased in severity during the DBTP. An AE that becomes serious during the DBTP will also be considered as NEAE. If more than 1 AE is reported before the first dose of IP in the DBTP and coded to the same preferred term, the AE with the greatest severity will be used as the benchmark for comparison with the AEs occurring during the DBTP that were also coded to that preferred term.

An AE (classified by preferred term) that occurs during the SFU of the study will be considered a newly emergent adverse event (NEAE) if the AE was not present before or at Visit 70 or it was present before or at Visit 70 and increased in severity during the SFU. An AE that becomes serious during the SFU will also be considered as NEAE. If more than 1 AE is reported before or at Visit 70 and coded to the same preferred term, the AE with the greatest severity will be used as the benchmark for comparison with the AEs occurring during the SFU that were also coded to that preferred term.

An AE that occurs more than 30 days after the date of the last dose of IP will not be counted as an NEAE.

An SAE that occurred between the date of the first dose of IP in the OLTP and 30 days after the date of the last dose of IP, inclusive, will be considered a treatment-emergent SAE (e.g., TESAE).

The overall number and percentage of patients with TEAEs, NEAEs, death, TESAEs, TEAEs leading to study discontinuation and TEAEs related to study drug during the OLTP will be tabulated overall, and during the DBTP and the SFU by treatment group.

The incidence of common ( $\geq 2\%$  of patients in any treatment group) TEAEs and NEAEs during the OLTP will be summarized overall by preferred term. Similarly, the incidence of common TEAEs and NEAEs during the DBTP and during the SFU will be summarized by preferred term and treatment group and will be sorted by decreasing frequency starting with the weekly rapastinel group followed by the clinically driven schedule rapastinel group.

Listings will be presented for all patients with AEs and patients who died (if any).

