**9.7.6.1 Adverse Events**

AEs will be coded by system organ class (SOC) and preferred term using the *Medical Dictionary for Regulatory Activities*.

An AE (classified by preferred term) that occurs during the OLTP or thereafter will be considered a treatment-emergent adverse event (TEAE) if it was not present before the date of the first dose of IP in the OLTP or was present before the first dose of IP in the OLTP and increased in severity during the OLTP or thereafter. If more than 1 AE is reported before the date of the first dose of IP in the OLTP and coded to the same preferred term, the AE with the greatest severity will be used as the benchmark for comparison with the AEs occurring during the OLTP that were also coded to that preferred term.

An AE (classified by preferred term) that occurs during the DBTP of the study will be considered a newly emergent adverse event (NEAE) if the AE was not present before the first dose of the double-blind IP or it was present before the first dose of the double-blind IP and increased in severity during the DBTP. If more than 1 AE is reported before the first dose of the double-blind IP and coded to the same preferred term, the AE with the greatest severity will be used as the benchmark for comparison with the AEs occurring during the DBTP that were also coded to that preferred term. An AE that occurs more than 30 days after the date of the last dose of IP will not be counted as a NEAE.

The number and percentage of patients reporting TEAEs during the OLTP will be tabulated by SOC and preferred term. Similarly, the number and percentage of patients reporting NAEs during the DBTP will be tabulated by SOC and preferred term. The number and percentage of patients in each treatment group reporting TEAEs and NAEs during the DBTP will be tabulated by SOC and preferred term; by SOC, preferred term, and severity; and by SOC, preferred term, and causal relationship to the IP. If more than 1 AE is coded to the same preferred term for the same patient during the same treatment period, the patient will be counted only once for that preferred term using the most severe and most related occurrence for the summarization by severity and by causal relationship to the IP.

The distribution of TEAEs and NAEs by severity and relationship to the IP will be summarized for each treatment group for the DBTP.

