The incidence of common ( $\geq 2\%$  of patients in any treatment group) TEAEs and NAEs during the DBTP will be summarized by preferred term and treatment group and will be sorted by decreasing frequency for the weekly rapastinel group.

An SAE that occurred between the date of the first dose of the open-label IP and 30 days after the date of the last dose of double-blind IP, inclusive, will be considered an on-therapy SAE. The number and percentage of patients who had on-therapy SAEs during the OLTP will be summarized by preferred term and sorted by decreasing frequency. The number and percentage of patients who had on-therapy SAEs during the DBTP will be summarized by treatment group and preferred term and will be sorted by decreasing frequency for the weekly rapastinel group.

The number and percentage of patients who had fatal on-therapy SAEs during the OLTP will be summarized by preferred term and sorted by decreasing frequency. The number and percentage of patients who had fatal on-therapy SAEs during the DBTP will be summarized by treatment group and preferred term and sorted by decreasing frequency for the weekly rapastinel group.

The incidence of TEAEs leading to premature discontinuation of IP during the OLTP will be summarized by preferred term and will be sorted by decreasing frequency. The incidence of TEAEs and NAEs leading to premature discontinuation of IP during the DBTP will be summarized by preferred term and treatment group and will be sorted by decreasing frequency for the weekly rapastinel group.

Listings will be presented for all patients with SAEs, patients with AEs leading to discontinuation, and patients who died (if any).

[REDACTED]

[REDACTED]

[REDACTED]

[REDACTED]

[REDACTED]

[REDACTED]

[REDACTED]

[REDACTED]

[REDACTED]

[REDACTED]

[REDACTED]

[REDACTED]

[REDACTED]

[REDACTED]

[REDACTED]

[REDACTED]

[REDACTED]

[REDACTED]

[REDACTED]

[REDACTED]

[REDACTED]

[REDACTED]

[REDACTED]

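### SAP 9.1 drops the newly emergent version of the related and discontinuation counts and, separately, moves the TEAE reference date to the lead-in study without recording the change

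*SAP*

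**What the plan says.** **TEAE reference date.** Protocol 9.7.6.1 calls an event treatment-emergent "if it was not present before the date of the first dose of IP in the OLTP", or if it became more severe afterwards. SAP 9.1 uses the same form of rule but a different date: "if it was not present before the date of the first dose of IP in the lead-in study".

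**NEAE definitions.** SAP 9.1 defines a newly emergent event for each period. The open-label version refers to the first OLTP dose. The double-blind version applies "if the AE was not present before the first dose of IP in the DBTP", or if the event became more severe after that dose.

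**What is tabulated.** For the two attributes at issue, the SAP provides that "TEAEs leading to study discontinuation and TEAEs related to study drug during the OLTP will be tabulated overall, and during the DBTP" and safety follow-up by treatment group; neither attribute has an NEAE counterpart. NEAEs are kept elsewhere: the overall patient counts include them, and "the incidence of common TEAEs and NEAEs during the DBTP and during the SFU will be summarized by preferred term and treatment group".

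**What the protocol planned.** Protocol 9.7.6.1 has both versions for both attributes in the double-blind period: "The incidence of TEAEs and NAEs leading to premature discontinuation of IP during the DBTP will be summarized by preferred term and treatment group", and "The distribution of TEAEs and NAEs by severity and relationship to the IP will be summarized for each treatment group for the DBTP". I read the protocol's NAE as the NEAE that it defines in the same section.

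**Change log.** SAP 15.0 says that output was limited to what an abbreviated report needs. The only major change it lists concerns the primary efficacy analysis.

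**The concern.** These are two separate defects.

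First, every randomized patient has had 8 to 16 weeks of open-label rapastinel, so the run-in is a source of carried-over events in all three arms. The double-blind NEAE definition separates those from events that are new or worse after randomization. The SAP applies it to the overall and common-event tables but not to the related and discontinuation counts, which readers rely on heavily when judging tolerability.

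Second, patients who received placebo or vortioxetine in the lead-in study start rapastinel only in the OLTP (protocol 9.1.1). With the reference date at the first lead-in dose, an event that began before they had any rapastinel can count as treatment-emergent during open-label rapastinel. The change alters what is counted, not just how much is printed, and SAP 15.0 does not mention it.

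**Working it through.** The plan states no figure to reproduce. The check applies the definitions to event histories, then shows the effect on a comparison under assumed rates.

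**Step 1: the rule.** For one preferred term, an event counts if its severity in the period exceeds the highest severity before the reference date (0 = absent). The reference dates are the first lead-in dose (SAP TEAE), the first OLTP dose (protocol TEAE and SAP open-label NEAE) and the first DBTP dose (double-blind NEAE). The SAP's extra provision for events that become serious is left out, because it does not distinguish these histories.

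**Step 2: an event reported in the double-blind period.**

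| History | SAP TEAE | Protocol TEAE | Double-blind NEAE |
|---|---|---|---|
| A. First seen in DBTP | yes | yes | yes |
| B. Seen in OLTP, same severity in DBTP | yes | yes | no |
| C. Seen in lead-in only, same severity in DBTP | yes | no | no |
| D. Seen in OLTP, worse in DBTP | yes | yes | yes |
| E. Seen before lead-in, same severity | no | no | no |

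B and C enter the SAP's double-blind related and discontinuation counts if the event has that attribute. Only C results from the lead-in reference date. B is a TEAE under the protocol too; what is missing for B is the NEAE row.

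**Step 3: an event reported in the open-label period.** Take an event absent before the lead-in, present on lead-in placebo or vortioxetine, and back at the same severity in the OLTP. It is a SAP TEAE, but neither a protocol TEAE nor a SAP open-label NEAE. It therefore enters the SAP's open-label TEAE, related and discontinuation counts and stays out of the open-label NEAE tables.

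**Step 4: consistency within the SAP.**
- SAP 9.1 starts the treatment-emergent SAE window at the first OLTP dose, not the first lead-in dose.
- SAP 14.5 sets missing severity to mild before the first open-label dose and to severe from then on. A lead-in event is thus imputed as if before treatment, while the TEAE rule treats the lead-in as on treatment.
- SAP 14.6 imputes missing causality only for events starting on or after the first open-label dose.
- SAP 14.7 builds incomplete event start dates around the same dose.

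The TEAE definition alone uses the lead-in date.

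**Step 5: illustration with assumed rates.** Suppose new related events occur in 3% on placebo and 8% on weekly rapastinel, and a share *c* of each arm has a carried-over related event, independently of new ones. The displayed rate is 1 − (1 − *c*)(1 − new rate). At *c* = 5%, placebo is 1 − 0.95 × 0.97 = 7.85% and rapastinel is 1 − 0.95 × 0.92 = 12.6%.

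| Carry-over | Placebo | Rapastinel | Ratio | Difference (points) |
|---|---|---|---|---|
| 0% | 3.00% | 8.00% | 2.67 | 5.0 |
| 2% | 4.94% | 9.84% | 1.99 | 4.9 |
| 5% | 7.85% | 12.60% | 1.61 | 4.75 |
| 10% | 12.70% | 17.20% | 1.35 | 4.5 |
| 20% | 22.40% | 26.40% | 1.18 | 4.0 |

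The absolute rates rise and the ratio shrinks; the difference changes little.

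**The case against.** The other side has several good points.

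- **The SAP already holds most of the remedy.** Its open-label NEAE is essentially the protocol's TEAE under another name, and NEAEs are tabulated overall and by common preferred term in both periods. This stands, and it confines the loss to the related and discontinuation counts. It does not supply those counts.
- **Abbreviated reporting.** SAP 15.0 says that output was reduced and claims to list only major changes. That can cover a dropped table. It does not cover a redefined TEAE.
- **Likely small numbers.** Randomized patients stayed on rapastinel for at least 8 weeks, so a recurrence of an event already tolerated that now leads to exit may be uncommon. This is plausible, and nothing in the documents settles it.

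A reader might also infer more than the documents support:

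- *That these events are charged to the wrong treatment.* A recurrence on placebo did happen on placebo, and relatedness is the investigator's judgement event by event. The visible text does not say whether an event occurs in a period by onset or by being ongoing; such a rule may stand in text not shown. What can be said is that these rows do not separate carried-over from new events.
- *That the lead-in reference date causes the open-label carry-over into the double-blind period.* History B shows that it does not.
- *That one arm is favoured.* Randomization is 1:1:1, so carry-over should be roughly balanced at the start of the double-blind period. The expected effect is dilution of ratios, not a shift toward a named arm.

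**Conclusion.** Both defects hold, and they are limited. The double-blind related and discontinuation counts lack the NEAE version that the protocol planned, so they mix carried-over with new events in every arm. The TEAE reference date departs from the protocol and from the SAP's own SAE and imputation rules, is not listed in SAP 15.0, and lets same-severity recurrences of lead-in placebo or vortioxetine events into the open-label TEAE, related and discontinuation counts.

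The size cannot be computed, because the documents give no adverse event rates. The table under Step 5 shows direction only, and rests on the assumed 3% and 8%, equal carry-over in both arms, and independence of carried-over and new events. The overall and common-event NEAE tables and the listings of all patients with adverse events are unaffected, and no efficacy result is touched. This is a cheap improvement, not a threat to the safety comparison as a whole.

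**What to change.** 1. In SAP 9.1, add rows for NEAEs leading to study discontinuation and NEAEs related to study drug, by arm in the double-blind period and overall in the open-label period, beside the TEAE rows. The NEAE flags are already defined. The double-blind rows restore what protocol 9.7.6.1 planned.
2. Reconcile the TEAE reference date with protocol 9.7.6.1, the treatment-emergent SAE rule in SAP 9.1 and the imputation rules in SAP 14.5 to 14.7. If the lead-in date is kept, give the reason and align or explain the other rules.
3. List any retained departure in SAP 15.0.

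Cost: a few table rows and some SAP wording. No new data are needed.
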